## 6.7. Concomitant Therapy

### 6.7.1. Permitted Medications

The following medications are permitted in this study:

- 1) Standard of care for the treatment of COVID-19 that are consistent with the NIH or WHO treatment guidelines.
- 2) Remdesivir, convalescent plasma therapy or hydroxychloroquine/chloroquine at approved doses
- 3) Dexamethasone at a stable dose  $\leq$  6 mg/day or other corticosteroids with the total daily dose equivalencies
- 4) Any medication or vaccine (including over-the-counter or prescription medicines, vitamins, and/or herbal supplements) that the patient has received within 30 days prior to enrollment or receives during the study period. However, patients cannot receive COVID vaccine during the study and within 30 days after the completion of this study.

The use of permitted medications will be documented in the patient's source documentation and the eCRF to include the following information:

- Reason for use
- Dates of administration including start and end dates
- Dosage information including dose, frequency, and route of administration
- Any changes in concomitant medications

The medical monitor should be contacted if there are any questions regarding concomitant or prior medication therapy.

### 6.7.2. Prohibited Medications

The following medications are prohibited in this study:

- 1) Chronic systemic use of corticosteroids within 2 weeks prior to screening at the following daily doses:
  - Methylprednisolone  $>32$  mg/day
  - Prednisone  $>40$  mg/day
  - Hydrocortisone  $>160$  mg/day
- 2) Use of immunosuppressant or immunomodulatory drugs within 1 month prior to screening, which include but not are limited to the following drugs:

Category	Medication
Interferon Alfa and Interferon Beta	Interferon Alfa, Interferon Beta

Interleukin-1 Inhibitor	Anakinra
Interleukin-6 Inhibitors	Sarilumab, Siltuximab, Tocilizumab
Bruton's Tyrosine Kinase Inhibitors:	Acalabrutinib, Ibrutinib, Zanubrutinib
Janus Kinase Inhibitor:	Baricitinib (Baricitinib at $\leq$ 4 mg/day for less than 7 days prior to screening is allowed. However, this medication should be discontinued after enrollment), Ruxolitinib, Tofacitinib

3) Any medications that are mainly metabolized by CYP450 2C19 will be excluded at screening and should not be used during the study for the treatment of AEs (See Appendix 6).

### **6.8. Treatment after the End of the Study**

At the EOS, the Investigator should advise patients to return to their primary care physician. Any reported AEs should be followed up.

## **7. Discontinuation of Treatment and Study**

### **7.1. Discontinuation of Treatment**

Study treatment for an individual patient will be up to 14 days (whether or not medication is taken) or until a treatment discontinuation criterion is met. Reasons for discontinuation of treatment include the following:

- Adverse Events
- Pregnancy
- Death
- Noncompliance resulting in protocol deviation
- Withdrawal of consent
- Investigator decision
- Other (specify)

A patient may withdraw from the study at any time at his/her own request, at the discretion of the investigator for safety, behavioral, or administrative reasons. If the patient withdraws consent for disclosure of future information, the sponsor may retain and continue to use any data collected before such a withdrawal of consent

Upon occurrence of a serious or intolerable AE where study treatment discontinuation is considered, the Investigator should confirm with the medical monitor. If a patient is discontinued because of an AE, the event will be followed until it is resolved, based on the medical judgement of the Investigator.

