### 6.3. Blinding and Unblinding

This is a double-blinded clinical trial. The placebo tablets will match the appearance of SIR1-365 tablets, and each patient will take one tablet, TID.

If a patient becomes seriously ill during the study, the blind will be broken for that patient only if knowledge of the administered study treatment will affect treatment options available to the patient. As soon as possible, the Investigator should first contact the medical monitor to discuss the medical

emergency and the reason for revealing the actual treatment received by that patient. The treatment assignment will be unblinded through the interactive response technology.

If the blind is broken, the date, time, staff involved, and reason must be recorded in the eCRF and any associated reports.

If a patient is unblinded for any reason, the study treatment will be discontinued. The patient will be followed through Day 28 or until early termination from the study.

During the study, unblinded safety, biomarker and clinical efficacy data will be reviewed by an IDMC.

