### **7.2.1. Follow-up for Patients Who Discontinued from Treatment/Study**

If the patients are discharged from the hospital before Day 14, it is preferred that the follow-up visit is in person to obtain safety laboratory tests and blood samples for biomarker analysis as well as clinical outcome data. However, infection control or other restrictions may limit the ability of the patients to return to the clinic. In this case, the follow-up visit may be conducted by phone and only safety data will be obtained.

Patients who complete the 14-day treatment should be instructed to have the scheduled follow-up visit on Day 28. If a patient determines he/she no longer wishes to participate in follow-up visit, all the procedures associated with Day 28/Early Discontinuation/End of Study (EOS) visit should be completed at the time of discontinuation.

In both cases, follow-up for AEs should occur as per the discretion of the investigator. It is vital to obtain follow-up data on any patient withdrawn because of an AE or SAE. In every case, efforts must be made to undertake protocol-specified safety follow-up procedures.

Refer to the schedule of assessments (SoA) for data to be collected at the time of study discontinuation, follow-up, and for any further evaluations that need to be completed.

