#### **8.2.2.1. Period and Frequency for Collecting AE and SAE Information**

All AEs and SAEs will be collected from the time when ICF is signed until the end of the patient's participation in the study.

All SAEs will be recorded and reported within 24 hours, as indicated in [Appendix 4](#). The Investigator will submit any updated SAE data within 24 hours of it being available. The SAE should be entered to EDC as defined in [Appendix 4](#).

Investigators are not obligated to actively seek AE or SAE in former study patients. However, if the Investigator learns of any SAE, including a death, at any time after a patient has been discharged from the study, and he/she considers the event to be reasonably related to the study treatment or study participation, the Investigator must promptly notify the sponsor.

The method of recording, evaluating, and assessing causality of AE and SAE and the procedures for completing and transmitting SAE reports are provided in [Appendix 4](#).

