## 10.3. Statistical Analyses

A detailed SAP will be developed and finalized before database lock.

A 2-sided alpha-level of 0.05 will be used for construction of confidence intervals. No adjustment for multiple endpoints will be employed. Although the study is not powered for hypothesis testing,

p-values will be generated to aid interpretation in addition to confidence intervals about the estimates.

The safety population will be the primary population for safety analysis. Analyses will be performed on observed data.

For clinical efficacy endpoints, the primary analysis will be in the ITT population. Rules for addressing missing data will be detailed in the statistical analysis plan. Sensitivity analyzes for the clinical efficacy endpoints may be performed in the mITT and/or PP populations.

The mITT population will be primary population for the biomarker analysis with exception of time to 50% reduction of CRP levels for which the ITT population will be primary. Sensitivity analyses incorporating imputation for missing biomarker values may be performed.

In general, baseline for each parameter is the last non-missing value collected prior to the first dose of study medication including pre-dose measurements made on the date of the first dose of study medication.

All data analyses will be conducted using SAS® (SAS Institute, Inc, Cary, North Carolina) software. In general, for descriptive summaries, continuous variables will be summarized using the mean, standard deviation, median, minimum value, and maximum value. Categorical variables will be summarized using frequency counts and percentages. All data will be presented in data listings.

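### Section 7.1 lets the investigator end a patient's study participation, not only study drug, so Day 28 vital status and efficacy outcomes are not secured after a safety withdrawal

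*Protocol*

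**What the plan says.** Protocol Section 7.1 covers discontinuation of treatment. Within it, patients are allowed to "withdraw from the study at any time at his/her own request, at the discretion of the investigator for safety, behavioral, or administrative reasons". The object of that sentence is the study, not the study drug. The same section adds that an AE behind a discontinuation is followed to resolution, as judged by the investigator.

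Section 7.2.1 deals with follow-up after discontinuation. It says "It is vital to obtain follow-up data on any patient withdrawn because of an AE or SAE", asks for efforts in every case to carry out the protocol's safety follow-up, and refers to the schedule of assessments. The follow-up column of that schedule doubles as the early-discontinuation visit (footnote 3) and includes oxygen use, WHO score and AEs.

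Section 8.2.2.1 ends AE and SAE collection when participation ends. After that, "Investigators are not obligated to actively seek AE or SAE in former study patients". A later SAE or death must be notified only if the investigator learns of it and considers it reasonably related to treatment or participation. Section 8.2.2.3 keeps SAEs and AEs of potential interest under follow-up until they resolve, stabilise or are explained, or the patient is lost.

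Section 6.3 says of an unblinded patient: "The patient will be followed through Day 28 or until early termination from the study".

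SAP Section 13.1.7 reports all-cause mortality to Day 28 as a proportion per arm with a Clopper-Pearson interval. It gives no rule for a patient whose Day 28 status is unknown.

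**The concern.** Stopping drug and leaving the study have different consequences for the data. A patient who only stops drug still contributes Day 28 outcomes. A patient who leaves the study does not, unless someone is told to look.

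Section 7.1 lets the investigator choose the second for safety reasons. In severe COVID-19, a patient withdrawn on those grounds is likely to have a different prognosis from one who stays, so the outcomes would not be missing at random. Three things are exposed:

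- 28-day all-cause mortality;
- the efficacy endpoints that run to Day 28 (WHO score, clinical improvement, days without oxygen, freedom from respiratory failure);
- the rule in Section 7.2 that halts enrolment after more than three deaths from any cause in the treatment group, which can count only the deaths that are known.

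**Working it through.** **Step 1. What survives a study withdrawal for safety reasons?**

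| Item | Still required? | Source |
|---|---|---|
| The AE that led to discontinuation | Yes, followed until resolved | Protocol 7.1 |
| SAEs and AEs of potential interest already reported | Yes, to resolution, stabilisation or explanation | Protocol 8.2.2.3 |
| Safety follow-up procedures | Efforts required | Protocol 7.2.1 |
| WHO score and oxygen use | At the early-discontinuation visit, not at Day 28 | Schedule of assessments, footnote 3 |
| New AEs or SAEs after withdrawal | Need not be actively sought | Protocol 8.2.2.1 |
| Death after withdrawal | Reported only if learned of and considered related, unless it is the outcome of an event already being followed | Protocol 8.2.2.1, 8.2.2.3 |
| Vital status, oxygen use and WHO score at Day 28 | Not secured by any passage | none |

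The last three rows are the gap.

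**Step 2. How does the SAP treat the gap?**

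- Mortality (13.1.7): no rule, although Protocol 10.3 leaves missing-data rules for efficacy endpoints to the SAP.
- WHO score at Day 28 (13.1.4): a missing value is imputed only from assessments after Day 14, so a patient withdrawn earlier has no Day 28 value.
- Time to clinical improvement (13.1.4.1): a patient without improvement is censored at the last assessment. That treats the withdrawal as uninformative.
- Respiratory failure (13.1.6): a patient with no post-baseline oxygen data counts as free of failure.

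**Step 3. Size for mortality.** The plan gives no figure to reproduce; the sample size is stated as not calculated. Let n = 30 per arm (Protocol 10.1), d = known deaths, m = patients of unknown Day 28 status.

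- Lower bound = d/n, upper bound = (d + m)/n, width = m/n.
- Each unknown patient adds 1/30 = 3.3 points.

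The documents give neither d nor m. Assume d = 3, so d/n = 3/30 = 10.0% (exact 95% CI 2.1% to 26.5%):

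| m | Lower bound | Upper bound | Width |
|---|---|---|---|
| 1 | 10.0% | 4/30 = 13.3% | 3.3 points |
| 2 | 10.0% | 5/30 = 16.7% | 6.7 points |
| 3 | 10.0% | 6/30 = 20.0% | 10.0 points |
| 5 | 10.0% | 8/30 = 26.7% | 16.7 points |

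At m = 3 the exact 95% CI for the upper bound of 6/30 is 7.7% to 38.6%. Without an SAP rule, the same data can also be reported in two ways: 3/30 = 10.0% if unknown is treated as alive, or 3/27 = 11.1% if unknown is dropped.

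**Step 4. Enrolment halt.** More than three deaths means the fourth death triggers it. With three known deaths in the treatment group, one death that nobody was required to find or report decides whether enrolment halts.

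**Step 5. Primary endpoint.** It is binary: any TEAE from baseline to Day 14. A patient withdrawn because of a TEAE already counts as an event, and later events cannot change that. Only a patient withdrawn before Day 14 with no TEAE so far has a shortened observation window.

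**The case against.** The strongest reply is that the protocol already protects these patients. Section 7.2.1 calls their follow-up data vital, the event behind the discontinuation is followed to resolution, reported SAEs are followed on, and a discontinuation visit collects WHO score and oxygen use. A death from the SAE that prompted withdrawal is therefore within required follow-up. All of this stands, and it narrows the gap to later, separate events and to Day 28 outcomes. It does not close it.

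Four stronger readings are tempting, and the documents do not support them:

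- *Safety withdrawals undercount the primary endpoint.* For patients withdrawn because of a TEAE they do not, as Step 5 shows.
- *Mortality is analysed only on observed cases.* The sentence "Analyses will be performed on observed data" in Protocol 10.3 follows directly on the statement about the safety population. Mortality is listed as an efficacy endpoint and analysed in the ITT set. Its problem is the absent SAP rule.
- *AE follow-up after a safety withdrawal is left to discretion.* The sentence "In both cases, follow-up for AEs should occur as per the discretion of the investigator" follows two named cases: patients discharged before Day 14, and completers who decline the follow-up visit. Neither is an AE withdrawal.
- *Section 6.3 contradicts 7.1.* It does not, because it carries its own exit for early termination from the study.

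It is also fair to say that the counts above are hypothetical, that the trial is exploratory and blinded, and that the direction of any bias depends on which arm has more such withdrawals. The intervals are wide even with complete data.

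**Conclusion.** The point holds in a limited form. Section 7.1 allows an investigator to end study participation for safety, behavioural or administrative reasons, and after that no passage secures Day 28 vital status, oxygen use or WHO score. AE follow-up is partly protected, and the primary endpoint is little affected. The exposure lies in 28-day mortality, the Day 28 efficacy endpoints and the any-cause death count for the enrolment halt.

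The size is 3.3 percentage points of an arm's mortality per patient of unknown status, or 6.7 to 10 points for two or three. This assumes 30 per arm and that such withdrawals occur; the documents give no expected number. No claim is made about which arm would be favoured. Because the remedy is cheap, the change should be made.

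**What to change.** In Section 7.1, separate the two actions:

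- The investigator may stop study treatment for the listed reasons, with the drug-stopping criteria unchanged. The patient then stays in the study for the assessments already scheduled to Day 28.
- Study withdrawal is limited to withdrawal of consent by the patient or legal representative, or loss to follow-up as defined in Section 7.3.
- For all randomised patients, Day 28 vital status is recorded from contact or records, where consent allows.

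Align Sections 7.2.1 and 8.2.2.1 with this. Appendix 5 requires immediate study withdrawal on pregnancy, while Section 8.2.2.5 and Appendix 5 itself require the pregnancy to be followed to outcome; these passages need to be reconciled. Since some statuses will remain unknown, SAP Section 13.1.7 should also say how they are handled and show best-case and worst-case bounds.

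The cost is a short wording change and a little more site follow-up for a few patients. No scheduled visit is added. SAP Section 10.1 already tabulates discontinuation of study drug and of study separately, so the distinction is already in use.

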#### Pre-specified Treatment Discontinuation Roles

- The presence of any of the following events may lead to treatment discontinuation based on the judgement of the site investigator with consultation with the medical monitor or IDMC: Patients started utilization of mechanical ventilation
- Patients experienced heart failure during the study
- Patients experienced respiratory failure during the study
- Patients experienced moderate to severe hepatic impairment during the study
- Patients experienced acute renal injury requiring dialysis during the study
- Any serious AE (SAE) assessed as related to study drug.

#### **7.2. Pause/Discontinuation of Study**

Enrollment in the study will be halting upon receiving reports of, until the IDMC is able to review the data and determine the safety of continuing with the study:

- Excess of two deaths in the treatment group which both the investigator and the IDMC agree are probably or definitely related to the investigational product.

or

- Excess of three deaths from any cause in the treatment group

In addition, any report of death or life-threatening SAE whose causal relationship to the study drug is judged to be probably or definitely related to investigational product by the treating investigator must be reviewed by the IDMC within 7 calendar days after sponsor is notified. If this does not happen, or there is not sufficient information provided for the IDMC to fully review the case, enrollment will be halted until such time as the IDMC can review the case and determine the safety of proceeding with the study.

The study could be stopped if:

- New information or other evaluation regarding the safety of the study drug indicates a change in the known risk profile for the study drug, such that the risk is no longer acceptable for patients participating in the study. The IDMC could recommend study termination based on pre-specified study stopping rules. However, the decision for study termination will be made by the Sponsor, the IRB, or Regulatory Authority
- The study is terminated by the Sponsor for administrative reasons.

If the Sponsor, the IRB, or Regulatory Authority decide to terminate or suspend the study or the participation of the investigational site, a study-specific procedure for early termination or suspension will be provided by the Sponsor. This procedure will be followed by the investigational site during termination or study suspension.

### **7.2.1. Follow-up for Patients Who Discontinued from Treatment/Study**

If the patients are discharged from the hospital before Day 14, it is preferred that the follow-up visit is in person to obtain safety laboratory tests and blood samples for biomarker analysis as well as clinical outcome data. However, infection control or other restrictions may limit the ability of the patients to return to the clinic. In this case, the follow-up visit may be conducted by phone and only safety data will be obtained.

Patients who complete the 14-day treatment should be instructed to have the scheduled follow-up visit on Day 28. If a patient determines he/she no longer wishes to participate in follow-up visit, all the procedures associated with Day 28/Early Discontinuation/End of Study (EOS) visit should be completed at the time of discontinuation.

In both cases, follow-up for AEs should occur as per the discretion of the investigator. It is vital to obtain follow-up data on any patient withdrawn because of an AE or SAE. In every case, efforts must be made to undertake protocol-specified safety follow-up procedures.

Refer to the schedule of assessments (SoA) for data to be collected at the time of study discontinuation, follow-up, and for any further evaluations that need to be completed.

### **7.3. Lost to Follow-Up**

A patient will be considered lost to follow-up if he or she repeatedly fails to complete scheduled visit procedures and is unable to be contacted by the study site.

The following actions must be taken if a patient is unable to complete a required study visit:

- The site must attempt to contact the patient and reschedule the missed visit as soon as possible and counsel the patient on the importance of maintaining the assigned visit schedule and ascertain whether or not the patient wishes to and/or should continue in the study.
- In cases in which the patient is deemed lost to follow-up, the Investigator or designee must make every effort to regain contact with the patient (where possible, 2 documented telephone calls and, if necessary, a registered letter to the patient's last known mailing address). These contact attempts should be documented in the patient's medical record.
- Should the patient continue to be unreachable, he/she will be considered to have withdrawn from the study with a primary reason of lost to follow-up.

## 8. Study Assessments and Procedures

Study procedures to assess safety, efficacy, biomarker and PK are shown in the SoA. Adherence to the trial requirements, including those specified in the SoA is essential for study conduct.

All screening evaluations must be completed and reviewed to confirm that potential patients meet all eligibility criteria within 2 weeks of clinically diagnosis of SARS-CoV-2 virus infection. The Investigator will maintain a screening log to record details of all patients screened and to confirm eligibility or record reasons for screening failure, as applicable.

Patients could be hospitalized for up to 14 days. Patients will be assessed daily while hospitalized. If the patients are discharged from the hospital before Day 14, all the assessments planned for Day 14 should be carried out before discharge. If a patient is still hospitalized after Day 14, no study drug will be administered after the last dose on Day 14.

It is preferred that the follow-up visit is in person to obtain safety laboratory tests. However, infection control or other restrictions may limit the ability of the patients to return to the clinic. In this case, the follow-up visit may be conducted by phone and only safety data will be obtained. Study drug will not be administered for early discharged patients.

To fit into the clinical practice of treating patients with severe COVID-19, screening visit and baseline visit can be combined in some patients. In that case, the number of dosing could be less than 3 times on that day. ECG, laboratory test and other test results obtained within 24 hours prior to consent can be used as baselines.

For those patients who complete the 14-day treatment period, the investigator will decide appropriate treatments for the period from Day 15 to Day 28.

A follow-up visit will be scheduled approximately on Day 28 ( $\pm 3$ ) or 14 ( $\pm 3$ ) days after the last dose for those who are discharged from the hospital before Day 14.

Procedures conducted as part of the patient's routine clinical management and obtained before signing of the Informed Consent Form (ICF) may be utilized for screening purposes, provided the procedures meet the protocol-specified criteria and are performed within the time frame defined in the Schedule of Assessments (SoA). Repeat or unscheduled tests or procedures may be performed for safety reasons or for technical issues.

Protocol waivers or exemptions are not granted under any circumstances. Major protocol deviations defined as events related to safety and/or integrity of study data must be discussed with the medical monitor immediately upon occurrence or awareness to determine if the patient should continue or discontinue study treatment.

